3.2.3 Exploratory Endpoints

The following exploratory endpoints will be evaluated:

- Change from baseline in SF-36 scores at each scheduled timepoint,
- Amount of rescue medication taken during the study,
- Time to first intake of rescue medication.

3.3 Study Duration

This study will consist of:

- A screening visit: 28 days maximum before IMP dosing,
- A Part A, pre-randomisation run-in period:
 - First injection test: 21 days maximum before IMP dosing,

- Second injection test: one week after first injection test, 14 days maximum before IMP dosing,
- A Part B, randomised double-blind period:
 - A baseline period including a QST and Actiwatch® training, safety assessments and a QoL: within 7 days before IMP dosing,
 - A one-day IMP dosing,
 - A 16-week randomised double-blind period.

Subjects are expected to participate in this study for a maximum of 20 weeks.

The study will be considered to have started when the first subject has provided signed informed consent and will be considered to have ended after the last subject has completed his EoS visit.

The overall study is anticipated to last approximately one year.

3.4 Randomisation and Blinding

3.4.1 Method of Randomisation

At screening, potential subjects will be allocated an 11-digit subject number consisting of:

- The country code (three digits),
- The centre number (three digits),
- The sequential order of entry of the subject in the unit (five digits).

3.4.1.1 Pre-randomisation Run-in Period (Part A)

Following confirmation of eligibility after the screening visit, subjects will be assigned to a pre-randomisation run-in number and allocated to one of the two treatment sequence groups in a chronological order, i.e. first eligible subject after the screening visit will be given the first run-in number (as detailed in [Table 1](#)). Subjects will be randomised with a ratio 2:2 (blocks of eight subjects) to receive:

- Either lidocaine on injection test 1 then placebo (saline) on injection test 2,
- Or placebo (saline) on injection test 1 then lidocaine on injection test 2.

Table 1 Part A Pre-randomisation Run-in Numbers

Part A Pre-randomisation Run-in Numbers
From CCI

3.4.1.2 Randomised Double-blind Period (Part B)

Subjects will be randomised to receive Dysport 2.5 U, Dysport 2.5 U placebo, Dysport 10 U, Dysport 10 U placebo, Dysport 20 U, Dysport 20 U placebo with a ratio 3:1:3:1:3:1 (blocks of 12 subjects).

Following confirmation of eligibility after injection test 2, subjects will be assigned to a randomisation number and allocated to one of the treatment groups in a chronological order, i.e. first eligible subject will be given the first randomisation number as detailed in [Table 2](#).

Table 2 Part B Randomisation Numbers

Part B Randomisation Numbers	Part B Replacement Randomisation Numbers
From CCI [REDACTED]	From CCI [REDACTED]

Mirror lists of randomisation numbers will also be produced to allow the randomisation of replacement subjects (e.g. the subjects who withdraw within six first weeks after IMP dosing) or to be used for the replacement of kits which could be damaged during the IMP reconstitution. For example, number CCI [REDACTED] will be used to randomise the replacement for the subject who was randomised with number CCI [REDACTED].

The sponsor's randomisation manager will prepare and keep the master lists of pre-randomisation run-in numbers and randomisation numbers. A copy of these lists will be sent confidentially to:

- Pharmaceutical Development Clinical Supply Chain
Beaufour Ipsen Industrie SAS
[name]
[name].

The lists and their copies will be kept confidential in secure locations. Access to the randomisation lists will be restricted until authorisation is given to release them for final analysis.

An identification code assigned to each subject will be used in lieu of the subject's name to protect the subject's identity when reporting AEs and/or other study-related data.

3.4.2 *Blinding*

Only the pharmacist or delegate in charge of drug preparation at the clinical research unit (CRU) and the monitor responsible for pharmacy monitoring will be partially unblinded. These personnel will be fully trained on the importance of their role in maintaining the blind for the subject, the investigator and the remainder of the study team. The unblinded staff at the CRU will not carry out any study assessments other than those they are assigned to.

All other staff at the CRU, the sponsor and the subjects will be blinded to treatment allocations during the study.

3.4.3 *Code-break*

Two types of code-break envelopes will be set up for the pre-randomisation run-in period (Part A) and for the randomised double-blind period (Part B).

Two sets of individual sealed code-break envelopes of each type will be prepared by the sponsor's randomisation manager to enable emergency code-break procedures for individual subjects without compromising the blind of the study. One set will be provided to the CRU and one set provided to the sponsor department of global patient safety (GPS).

In an emergency situation, which requires the identification of the study treatment group, the investigator may break the treatment code. If so, the investigator is requested to:

- Inform the monitoring office at the earliest opportunity that the blind has been broken for an emergency situation,
- Reseal the code-break envelope,
- Sign, date and provide reason for the code-break on the emergency code-break form, and on the sealed envelope.

The date and reason for code-breaking should also be recorded in the electronic case report form (eCRF).

Specific case, to check if the subject is a responder at the end of the run-in period, the investigator will unblind the subject by (re)-opening the code-break-envelope associated to his/her assigned pre-randomisation run-in number. The investigator will sign, date and specify "End of run-in period" as the reason for the code-break on the envelope.

Monitors should routinely check the integrity of the envelopes that are stored at the study site. They must collect envelopes from the study site prior to study close-out and ensure that they are all intact. If envelope(s) have been opened at the site or by the sponsor's representative, the monitor must ensure a written explanation is clearly documented (opener's name, dated signature and reason for opening) on the visit status page of the eCRF.

Confirmation of the integrity of all code-break envelopes at study completion must be documented in the trial master file (TMF). All sets of the sealed individual subject envelopes must be kept in the TMF in the co-ordinating office at study completion for proof of integrity.

3.5 Stopping Rules and Discontinuation Criteria

The complete study can be terminated prematurely at any time if the sponsor judges it necessary for any reason. In that case, all scheduled procedures and assessment for subjects who are still in the study will be performed.

Some possible reasons for the closure of a study site may include:

- Failure of the investigator staff to comply with the protocol or with the GCP guidelines,
- New and significant safety concerns,
- Inadequate subject's recruitment.

During the conduct of the study, all AEs including serious AEs (SAEs) will be reviewed as they are reported from the study site to identify new and significant safety concerns.

3.6 Source Data Recorded on the Case Report Form

Data will be collected in the eCRF in compliance with Food and Drug Administration (FDA) 21 CFR Part 11. As required by GCP, the sponsor assigned monitor will verify, by direct reference to the source documents, that the data required by the protocol are accurately reported on the eCRF. The source documents must, as a minimum, contain a statement that the subject is included in a clinical study, the date that informed consent was obtained prior to participation in the study, the identity of the study, diagnosis and eligibility criteria, visit dates (with subject status), agent and IMP administration, and any AEs and associated concomitant medications.

Definitions for source data and source documents are given below:

- **Source data:** All original records and certified copies of original records of clinical findings, observations, or other activities necessary for the reconstruction and evaluation of the study. Source data are contained in source documents (original records or certified copies).
- **Source documents:** Original documents, data and records (e.g. hospital records, clinical and office charts, laboratory notes, memoranda, subjects' diaries or evaluation checklists, pharmacy dispensing records, recorded data from automated instruments, copies or transcriptions certified after verification as being accurate copies, microfiches, photographic negatives, microfilm or magnetic media, X-rays, subject files, and records kept at the pharmacy, at the laboratories and at medicotechnical departments involved in the clinical study).

No source data will be directly recorded on the eCRF during the present study.

4 SELECTION AND WITHDRAWAL OF SUBJECTS

4.1 Inclusion Criteria

Subjects must fulfil all of the following criteria to be considered eligible for enrolment in the study.

- (1a) Male and female subjects aged between 18 and 75 years inclusive at the time of giving informed consent.
- (2) Subjects suffering from an area of chronic pain post-abdominal or thoracic surgery, chronic abdominal or thoracic scar pain.
- (3) Longitudinal axis of the pain area of 10 cm long maximum (as mapped upon screening).
- (4) Subjects with moderate to severe pain, i.e. spontaneous NRS score of 4-8 which has been stable for the previous month before screening.
- (5) Stable use of analgesics (or any medication impacting pain perception) during the month before screening and expected to be stable for the study duration.
- (6) Under stable medication regimen for other medication, i.e. during the month before screening.
- (7a) Time from surgery which caused the painful scar more than six months and less than ten years at screening.
- (8) No other distracting pain either chronic or acute.
- (9) Female subjects of childbearing potential must have a negative urine pregnancy test result and be willing to use reliable contraceptive measures throughout study participation. Reliable forms of contraception include but are not limited to hormonal contraceptives (e.g. oral, patch, injection), double-barrier (e.g. male condom plus spermicide, or female diaphragm plus spermicide), intrauterine device, male partner has had a vasectomy, total abstinence from intercourse with male partners (periodic abstinence is not acceptable). Female subjects meeting any of the following criteria are not considered to be of childbearing potential: postmenopausal (≥ 47 years of age and amenorrhoeic for at least 12 consecutive months), have been sterilised surgically (e.g. bilateral tubal ligation), have had a hysterectomy, have had a bilateral oophorectomy.
- (10) The subject's primary care physician has provided evidence which can be used to confirm that within the last 12 months of dosing that there is nothing in their medical history that would preclude their enrolment into a clinical study.

4.2 Exclusion Criteria

Subjects who meet any of the following criteria will not be considered eligible for enrolment in the study.

- (1) Previous treatment with BTX (any serotype) during the past six months before screening.
- (2) History of hypersensitivity to any of the components of the Dysport formulation (which includes human serum albumin and lactose) or allergy to cow's milk protein.
- (3) Known hypersensitivity to lidocaine or other anaesthetics of the amide type, known hypersensitivity to hydroxybenzoates, complete heart block, hypovolaemia.
- (4) Any medical condition that may put the subject at risk with exposure to BTX, including diagnosed myasthenia gravis, Eaton-Lambert syndrome, amyotrophic lateral sclerosis, or any other disease that might interfere with neuromuscular function.
- (5) Opioid analgesic use at a Morphine Equivalent Dosage (MED) of >75 mg per day.
- (6) Neuroma in the scar pain area, diagnosed per ultrasound.

- (7) Use of agents that could interfere with neuromuscular transmission, including calcium channel blockers, penicillamine, aminoglycosides, lincosamides, polymixins, magnesium sulphate, anticholinesterases, succinylcholine and quinidine.
- (8) Need of any prohibited medication.
- (9) Any abnormal laboratory value, physical examination, vital signs, or electrocardiogram (ECG) that, in the opinion of the investigator, is clinically significant and that would compromise the safety of the subject in the study.
- (10) Positive for hepatitis B antigen or hepatitis C virus ribonucleic acid, positive results for human immunodeficiency virus, or who receives diagnosis for acquired immunodeficiency syndrome.
- (11) Positive urine screen for drugs of abuse (except for cotinine and unless explained by the investigator for therapeutic use of medication) or any history of drug or alcohol abuse, misuse, physical or psychological dependence, mood changes, sleep disturbance and functional capacity which have an impact on pain perception.
- (12) Significant neurological or psychiatric disorders including mental instability (unrelated to the pain) that could interfere with pain assessments; other pre-existing pain syndromes, acute or chronic, that might impair the assessment of the scar pain.
- (13) Any medical history of significance and/or inadequately controlled such as cardiovascular (e.g. uncontrolled high blood pressure, high risk of cardiovascular events, severe heart failure), pulmonary (e.g. uncontrolled asthma or emphysema), haematologic, (e.g. coagulopathy/bleeding disorders), neurological (e.g. swallowing problems, blurred or double vision, trouble saying words clearly (dysarthria), hoarseness or change or loss of voice (dysphonia)), liver disease (e.g. severe hepatic impairment), kidney disease (e.g. impaired renal function in subjects taking diuretics, angiotensin converting enzyme (ACE)-inhibitors, or angiotensin II antagonists), endocrine, immunologic, dermatologic painful conditions or any other conditions that may compromise in the opinion of the investigator the ability of the subject to participate in the study.
- (14) If in the investigator's opinion there are any factors that may confound the analysis of the study regarding efficacy and safety (e.g. an NRS > 9).
- (15) Previous randomisation in this study.
- (16) Subjects who participated in a clinical research study involving a new chemical entity or an experimental drug within 30 days before screening.
- (17) Subjects who are incapable of complying with the protocol in the judgment of the investigator.

4.3 Rationale for Specific Inclusion / Exclusion Criteria

Mapping of the painful area is to detect the anatomical relationship to the scar and the previous surgery, and to ensure that the longitudinal axis of the pain area length will be consistent with the injection paradigm. Pain area should be large enough to have a minimum of 4 injections and a maximum of 10 injections. This maximum of 10 injections is set so as not to exceed the maximum permitted dose (200 U of Dysport) with the highest dose (20 U). This in turn limits the maximum length of the painful area to 10 cm, with five injections, 2 cm apart, either side of the longitudinal axis of the pain area, and an estimate of approximately 1 cm spread of dose around each injection point.

4.4 Withdrawal of Subjects

In accordance with the declaration of Helsinki and International Council for Harmonisation (ICH) GCP, each subject is free to withdraw from the study at any time, for any reason (e.g. withdrawal of consent, AE).

The investigator can withdraw a subject from the study at any time for any reason (e.g. protocol deviation, non compliance with the protocol conditions, lack of cooperation, in the event of concurrent illness, AE, or other reasons concerning the health or well-being of the subject).

The reason for and date of withdrawal from the study must be recorded in the eCRF.

If withdrawal is based on subject's decision every attempt will be made to determine:

- The reason for withdrawal,
- Whether the subject also decides to withdraw his/her consent for the sponsor to collect and use the data collected up to the withdrawal point.

Data collected prior to subject withdrawal may be kept in study records and shared for further analyses unless the subject formally specifies his/her decision to withdraw consent for using data already collected.

Should a subject be withdrawn from the study after IMP dosing and before normal study completion, all efforts will be made to complete the EoS assessments and report the observations up to the time of withdrawal as thoroughly as possible. A complete final evaluation at the time of the subject's withdrawal should be made whenever possible.

Subjects who withdraw within the first six weeks after IMP dosing for reasons other than lack of efficacy will be replaced. Replacement subjects will receive the same schedule and treatment as the subject they have replaced.

5 STUDY CONDUCT

5.1 Study Schedule of Assessments

The schedule of procedures and assessments during the study is summarised and presented in Section 18.1. Subjects will be monitored throughout the study with review of their pain scores at both telephone and physical visits to site. In addition, the subjects can contact the site at any time and if required an unscheduled visit can be performed to assess the subject and their participation in the study.

The total volume of blood drawn for each subject and all evaluations throughout this study is detailed and presented in Section 18.2.

5.2 Study Visits and Procedures

All screened subjects must be identifiable throughout the study. The investigator will maintain a list of all subjects screened with subject numbers and names to enable records to be found at a later date if required. Records up to the time of premature termination or normal study completion should be completed. In the event that a subject is a screen failure (fails after screening visit) or is a run-in failure (withdraws in the run-in period), the primary reason will be recorded.

During the screening visit and pre-randomisation run-in period (Part A), tests and assessments will be performed to check compliance with inclusion/exclusion criteria and study requirements in order to confirm each subjects' eligibility prior to enrolment in Part B.

The screening and pre-randomisation run-in procedures/evaluations detailed in Section 18.1 will be performed during several out-patient visits.

5.2.1 Screening

The subjects will attend the CRU for a screening out-patient visit within 28 days prior to IMP dosing on Day 1.

5.2.1.1 Informed Consent

After a subject has received explanations and responses to his potential questions about the study by the investigator (or designee) and has been given reasonable time read and consider the patient information sheet, a signed and dated informed consent form will be completed with an investigator prior to any study procedures.

5.2.1.2 Screening Procedures

After informed consent is obtained, subjects will be allocated a study-specific subject number which must comply with formatting specifications provided by the sponsor (see Section 3.4.1) and will undergo screening assessments.

5.2.2 Pre-randomisation Run-in Period (Part A)

After successful screening of medical eligibility and within 21 days maximum before IMP dosing on Day 1, subjects will come back to the CRU for an injection test 1 visit, they will receive a pre-randomisation run-in number and be injected in a double blind fashion with either local anaesthetic (lidocaine) or placebo (saline).

They will be assessed for pain perception on site and then be discharged from the CRU from 1 hour post-injection test 1 and continue to record their NRS score at home as described in Section 9.1.2. They will be contacted by telephone by the site to check their safety and collect

their NRS score post-injection test 1 at the end of the injection test 1 day and on the following day.

Approximately one week later and within 14 days maximum before IMP dosing on Day 1, they will come back to the CRU for injection test 2. They will be crossed over and injected with the other agent.

They will be assessed for pain perception on site and then be discharged from the CRU from 1 hour post-injection test 2 and continue to record their NRS score at home as described in Section 9.1.2. They will be contacted by telephone by the site to check their safety and collect their NRS score post-injection test 2 at the end of the injection test 2 day and on the following day. After completion of subject's injection test 2, the blind will be broken by an investigator to check if the subject is a responder.

Subjects will be considered as responders and randomised to Part B if:

- The pattern of pain relief is sufficiently greater with lidocaine than saline using the formula below:

$$[\text{NRS}_{\text{predose}} - \text{NRS}_{\text{1 hour post-injection test}}]_{\text{placebo}} - [\text{NRS}_{\text{predose}} - \text{NRS}_{\text{1 hour post-injection test}}]_{\text{lidocaine}} \geq 2$$
- The pattern of pain relief is clinically plausible in the investigator's opinion, e.g. onset of pain relief reported by 30 min from time of completing the injections, pain scores after the lidocaine injection test rising again by 2-8 hours post-injection,
- The investigator has no concern regarding compliance with study procedures and safety.

Albeit considered unlikely, should the results be equivocal, or if an unexpected but plausible pattern of response emerges, the decision as to whether a subject should proceed in the study, will be adjudicated by mutual agreement of the investigator and the sponsor.

Subjects will be contacted by telephone by an investigator to inform them of the result. If subjects are assessed as responders and there are no concerns over subject safety, compliance with study assessments, they will enter in Part B.

The scheduled dates should be with sufficient time between study visits test 1, test 2 and baseline. This is to permit the scar area to return to baseline after examination, test dosing or QST procedures.

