1.7 Population to be Studied

This study will enrol male and female subjects with a painful abdominal or thoracic scar. Pain should be rated as moderate to severe i.e. numerical rating scale (NRS) score between 4 and 8 on an 11-point scale (0-10), and stable within one month before screening. The pain should also be chronic, i.e. persistent for more than six months after the surgery which led to the painful scar.

To ensure subjects will potentially benefit from intradermal injection of Dysport, they will be tested for responsiveness to local anaesthetic (lidocaine) during a pre-randomisation run-in period. This is consistent with use of diagnostic local anaesthetic blocks which are used to obtain information about of the source of subject's pain, being target specific and controlled in order to exclude false positive results (Bogduk, 2002). This assessment will be performed by investigators with experience in managing subjects with painful conditions and pain studies.

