18 ATTACHMENTS

18.1 Attachment 1 – Study Schedule of Assessments

Study Procedures	Screening D-28 max	Injection test 1 D-21 max	Injection test 2 D-14 max	Baseline from D-7 max	D1 pre- dose	D1 post- dose	D2-D7	W2 [a]	W4 [a]	W6 [a]	W8 [a]	W10 [a]	W12 [a]	W14 [a]	W16 EoS/ ED [a]
Part	Screening	Part A		Part B											
Informed consent	X														
Clinic visit	X	X	X	X	X					X			X		X
Subject call		X [b]	X [b]	X [c]			X [d]	X [d]	X [d]		X [d]	X [d]		X [d]	
Eligibility check	X			X	X										
Demography	X														
Medical and surgical history	X														
Drug of abuse	X														
Urine pregnancy test (female subjects only)	X				X										X
Physical examination	X			X	X					X [f] [g]					X
Vital signs	X [e]	X [g]	X [g]	X [g]	X [g]	X [g]				X [g]					X [g]
ECG, Safety lab	X														
Scar ultrasound	X														
Painful area mapping	X	X	X	X	X [h]					X			X		X

Study Procedures	Screening D-28 max	Injection test 1 D-21 max	Injection test 2 D-14 max	Baseline from D-7 max	D1 pre-dose	D1 post-dose	D2-D7	W2 [a]	W4 [a]	W6 [a]	W8 [a]	W10 [a]	W12 [a]	W14 [a]	W16 EoS/ ED [a]
Pre-randomisation Part A		X													
Lidocaine/placebo injection (saline)		X	X												
NRS score collection and diary providing		X [i]	X [i]												
Actiwatch® training and providing				X											
Randomisation in Part B					X										
Dysport/placebo injections						X									
Spontaneous NRS	X [j]	X [k]	X [k]	X [l]	X [l]	X [l]	X [l]	X [l]	X [l]	X [l]	X lk]	X [l]	X [l]	X [l]	X [l]
Rescue medication diary provided						X									
Reminder about analgesia washout 12-hour period pre-injections or QST		X	X	X	X			X	X	X	X	X	X	X	
QST (stimulus-evoked NRS)				X [m]						X [m]			X [m]		
QoL (SF-36)				X						X			X		
Concomitant medications and adverse events	X	X	X	X	X	X	X	X	X	X	X	X	X	X	X

a Visit to be performed \pm 3 days around the scheduled date.

b In the evening and on the following morning to check safety and collect spontaneous NRS scores.

- c Once the NRS scores from injection tests 1 and 2 are known and blind has been broken, the subject's responder status is determined. Subjects will be contacted by telephone by an investigator to inform of the result, and in the case of responders, they will enter in Part B.
- d Subjects will be contacted by telephone by the CRU every day up to Day 7 and every 2 weeks after IMP dosing for collection of AEs, concomitant medications and compliance with pain assessments and other study requirements.

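### Part A pain scores are collected blind, but responder status is decided after the investigator opens the code, so unblinded opinion and adjudication affect who enters Part B

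*Protocol*

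**What the plan says.** Three places in the protocol give the same order of events.

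- Section 5.2.2: "After completion of subject's injection test 2, the blind will be broken by an investigator to check if the subject is a responder".
- Section 3.4.3, as a specific case: "the investigator will unblind the subject by (re)-opening the code-break-envelope associated to his/her assigned pre-randomisation run-in number".
- Note c to the schedule in 18.1: "Once the NRS scores from injection tests 1 and 2 are known and blind has been broken, the subject's responder status is determined".

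Section 5.2.2 then lists three conditions for being a responder. The first is numeric, based on the change in NRS from predose to 1 hour under each agent. The second is opinion: "The pattern of pain relief is clinically plausible in the investigator's opinion". The third is that the investigator has no concern about compliance or safety. Equivocal results, or unexpected but plausible ones, take another route: the decision "will be adjudicated by mutual agreement of the investigator and the sponsor".

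Section 1.7 justifies the lidocaine test by analogy with diagnostic blocks, described as "being target specific and controlled in order to exclude false positive results". Section 3.4.2 names the pharmacist (or delegate) and the pharmacy monitor as the only partially unblinded people and adds: "All other staff at the CRU, the sponsor and the subjects will be blinded to treatment allocations during the study". It does not mention the routine Part A code-break. Section 3.4.1.1 gives the Part A allocation: "Subjects will be randomised with a ratio 2:2 (blocks of eight subjects) to receive".

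**The concern.** A saline control guards against false positives most fully when the person judging the pattern does not know which curve belongs to lidocaine. Here that person has just opened the envelope. The plausibility example in 5.2.2 is itself worded for someone who knows the code, since it refers to scores after the lidocaine test. An investigator who expects lidocaine to work may read an odd time course more generously, or more strictly, once the label is known. The adjudication route carries no requirement that either party be blinded.

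What is at stake is the meaning of lidocaine responder, the label that defines the Part B population. With six subjects per arm, one subject is 1/6, or about 17%, of an arm's mean. A few entries or rejections that turn on unblinded opinion would make it less clear to whom a positive or null result applies.

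**Working it through.** **1. Order of events.** Section 9.1.2 has current-pain scores taken predose, at 30 minutes, at 1 hour, hourly to 8 hours and between 20 and 24 hours, for each test. Note c puts the code-break after the scores of both tests are known and the decision after the code-break. So measurement is blind and classification is not.

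**2. What each unblinded element can do.** Section 5.2.2 lists the criteria without an explicit connective; I read them as joint.

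- *Opinion (plausibility, compliance):* it can veto a subject who meets the numeric criterion. It cannot admit one who fails it.
- *Adjudication:* it can admit a numeric failure or reject a numeric success.

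**3. The numeric criterion as printed.** Write R for predose NRS minus 1-hour NRS. The formula requires R(placebo) − R(lidocaine) ≥ 2. Its lead-in sentence requires relief to be sufficiently greater with lidocaine. If R(lidocaine) exceeds R(placebo), the printed difference is negative and the subject fails. The two statements contradict each other. Until they are reconciled the objective criterion cannot be applied as written, and more weight falls on the unblinded judgement.

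**4. Size of the selection step.** The protocol expects about 60 subjects in Part A and 24 randomised. 60 − 24 = 36, and 36/60 = 60% not randomised for all reasons combined. The documents do not say how many of these would be opinion vetoes. SAP 5.2 counts non-responders and SAP 5.7.2 lists NRS data; neither separates numeric failures from opinion or adjudication.

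**5. Predictability within blocks (secondary).** Inputs: blocks of eight, four per sequence, chronological allocation (3.4.1.1), and all C(8,4) = 70 orders equally likely. If every earlier code in the block is open:

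- expected number of certain sequences = 2×4/(4+1) = 1.6 of 8 (20%);
- expected correct best guesses = 4 + (2^8/70 − 1)/2 = 5.33 of 8 (66.6%, against 50%).

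Sixty subjects make seven full blocks and a half block. No sequence can be certain before position 5, so the half block adds none: 7 × 1.6 = 11.2, about 11 of 60.

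Enumeration of the 70 orders, with the most recent subjects' codes still closed:

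| Recent codes still closed | Certain per block | Best-guess rate |
|---|---|---|
| 0 | 1.6 (20%) | 66.6% |
| 1 | 0.6 (7.5%) | 60.4% |
| 2 | 0.17 (2.1%) | 57.7% |
| 3 | 0.03 (0.4%) | 55.0% |
| 4 | 0 | 53.4% |

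The documents give no accrual rate. Assuming 60 subjects over 32 to 48 weeks gives 1.25 to 1.9 per week. With about 8 days from test 1 to code-break, that leaves 1.4 to 2.1 earlier subjects still coded at a subject's test 1. The certain share is then roughly 2% to 8% at test 1. By test 2 nearly all lower-numbered codes are open and the share approaches 20%.

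**The case against.** Much can be said for the plan, and most of it stands.

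- *The test is still controlled.* A reader might infer that the run-in is neither blinded nor controlled. The documents do not support this: agents are given double-blind, each subject is their own saline control, and that subject's scores precede the code-break.
- *Opinion cannot wave false positives through.* A reader might infer that it can. Under joint criteria it can only reject. Admission against the formula needs adjudication, which 5.2.2 calls unlikely and which requires the sponsor's agreement.
- *The code-break is disclosed.* Section 3.4.3 describes it, with separate Part A and Part B envelopes and a recorded reason. The conflict with 3.4.2 is a missing cross-reference, not a concealed practice.
- *Block prediction is limited.* Sixty non-overlapping subjects at 8 days each would need 480 days, against a study of about one year, so the 20% figure cannot hold throughout at test 1. The documents do not say that whoever opens envelopes also collects the 1-hour score, so influence on later subjects' scores is conjecture.
- *Part B is untouched.* It has its own randomisation list, and its analysis is descriptive with no tests. A reader might infer that Part B allocation or comparability is compromised; nothing in the documents supports that.

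These points do not answer the central one. Plausibility and compliance are judged with the code known, although the data needed to judge them are available before it is opened.

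**Conclusion.** The point holds in a limited form. The Part A responder decision, as distinct from the Part A measurements, is unblinded. Opinion with the code known can remove numeric responders, and adjudication with the code known can add numeric non-responders. This weakens the stated aim of excluding false positives and makes the selected population less well defined. It does not bias the comparison between Part B arms.

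The number of subjects affected cannot be derived from the documents. The conclusion rests on reading the three criteria as joint and on note c's order being followed. Block predictability is a minor addition: at most 1.6 of 8 sequences certain, about 11 of 60, and about 2% to 8% at test 1 under the assumed accrual. The contradiction between the printed formula and its lead-in sentence is a separate defect that must be resolved before the numeric criterion is used.

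**What to change.** 1. In 5.2.2, 3.4.3 and note c, require the investigator to record and sign, before the envelope is opened and separately for test 1 and test 2, whether the pattern is plausible and whether there is any compliance concern. The scores in 9.1.2 already supply what is needed.
2. Open the code only to apply the numeric criterion, after the formula and its lead-in sentence have been reconciled.
3. Document any adjudication as made after unblinding, and list those subjects separately.
4. State the Part A code-break as an exception in 3.4.2, with a reference to 3.4.3.

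The cost is one extra source form, some wording, and a plausibility rating made for both tests without the code. An investigator may still guess the agent from a marked difference between tests.

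This does not remove predictability within blocks, because codes are still opened at the site. Having the pharmacist return only responder or not responder would not remove it either: once the investigator has recorded a difference of at least 2 points between tests, that answer reveals the sequence of every subject whose code is consulted.
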